8.2 Randomization

Not applicable.

8.3 Endpoints

8.3.1 Primary Endpoint

The primary endpoint for Part A of the trial is the confirmed BOR, per RECIST 1.1, as determined by an IERC and defined as the best response obtained among all tumor assessment visits after start of trial treatment until documented disease progression, excluding assessments after start of subsequent anticancer therapy, taking into account the following requirement for confirmation: PR or CR needs to be confirmed at a subsequent tumor assessment, preferably 6 weeks after the initial observation of response and according to the normal 6-week assessment schedule (or a subsequent assessment for PR), but no sooner than 5 weeks after the initial documentation of CR or PR.

For Part B, the primary endpoint is durable response, defined as objective response (CR or PR) according to RECIST 1.1, determined by an IERC, with a duration of at least 6 months. Duration of response will be calculated as specified in Section 8.3.2. Subjects for whom the duration of response is censored will be treated as failures (successes) in the analysis of durable response if the censored duration of response is below (at least) 6 months, respectively.

The date of a tumor assessment is defined as the earliest lesion measurement date corresponding to the respective visit that is documented in the eCRF. Details of determination of tumor response date at each time point will be provided in IERC charter document.

8.3.2 Secondary Endpoints

The duration of response will be calculated for each subject with a confirmed response as the time from first observation of response until first observation of documented disease progression or death within 12 weeks of the last tumor assessment, whichever occurs first.

For subjects with a confirmed response but neither documented disease progression nor death within 12 weeks after the last tumor assessment, as of the cut-off date for the analysis, the duration of response will be censored at the date of the last tumor assessment. Detailed censoring rules for duration of response can be found in [Table 9](#) for Part A and in [Table 11](#) for Part B.

The response status at 6 and 12 months after start of trial treatment according to RECIST 1.1 (as determined by the IERC) will be determined. A subject will be considered to be in response at the given timepoint (6 or 12 months after the start of the subject’s treatment) if the subject had a documented response (PR or CR) prior to that timepoint, and neither died nor experienced disease progression according to the RECIST 1.1 nor was lost to follow-up up to the given timepoint.

The PFS time, according to the RECIST 1.1, will be defined from first administration of trial treatment until first observation of PD or death within 12 weeks of the last tumor assessment or first administration of trial treatment (whichever is later). Details on determination of the first disease progression date will be specified in the IERC charter.

If a subject has neither a progression date nor a death date within 12 weeks after the last tumor assessment as of the data inclusion cut-off date for the analysis, the PFS time will be regarded as censored on the date of last known tumor assessment, or date of the first administration of trial treatment if the subject does not have any postbaseline tumor assessment. In Part B, PFS time will be regarded as censored on the date of last adequate tumor assessment (ie, having a result that is not non-evaluable or not available) if the subject begins a new anticancer therapy.

For Part A, subjects with both of the following conditions fulfilled, the general censoring rules apply as presented in [Table 9](#).

- Baseline tumor assessment
- At least one tumor assessment after start of treatment

Table 9 Part A: General Censoring Rules for Progression-free Survival and Duration of Response

		Date of event / censoring	Censoring
PD according to RECIST as assessed by the IERC		Date of PD	No
No PD	If death within 12 weeks after last tumor assessment or first administration of trial treatment	Date of death	No
	If death not within 12 weeks after last tumor assessment or first administration of trial treatment	Date of last known tumor assessment	Yes

IERC=Independent Endpoint Review Committee, PD=progressive disease.

For Part A, subjects with no tumor assessment at baseline or no tumor response assessment postbaseline, the special censoring rules as presented in [Table 10](#), which overrule the general censoring rules, apply.

Table 10 Part A: Special Case Censoring Rules for Progression-free Survival

		Date of event / censoring	Censoring
No tumor assessment at baseline	If death within 12 weeks after first administration of trial treatment	Date of death	No
	If death not within 12 weeks after first administration of trial treatment	Date of first administration of trial treatment	Yes
No tumor response assessment post baseline	If death within 12 weeks after first administration of trial treatment	Date of death	No
	If death not within 12 weeks after first administration of trial treatment	Date of first administration of trial treatment	Yes

For Part B subjects, the censoring rules for PFS and duration of response are presented in [Table 11](#).

Table 11 Part B: Outcome and Event Dates for Progression-free Survival and Duration of Response Analyses

Scenario	Date of event / censoring	Outcome
No baseline assessment	Date of first study treatment	Censored ^a
Progression or death \leq xx weeks after last tumor assessment or \leq xx weeks after treatment start date, where xx is 12 weeks through 12 months from start of treatment, and 24 weeks thereafter.	Date of progression or death	Event
Progression or death $>$ xx weeks after the last tumor assessment, where xx is 12 weeks through 12 months from start of treatment, and 24 weeks thereafter.	Date of last adequate tumor assessment	Censored
No progression	Date of last adequate tumor assessment	Censored
Treatment discontinuation due to “Disease progression” without documented progression	Not applicable	Information collected on treatment discontinuation page is ignored since outcome should be derived based on documented progression only. General censoring rule is applied.
New anticancer therapy given	Date of last adequate tumor assessment before anticancer therapy is given	Censored

^a However if the subject dies \leq 12 weeks after treatment start date the death is an event with date on death date.

The OS time will be defined as the time from first administration of trial treatment until the date of death. The OS time is considered a key secondary endpoint.

For subjects who are still alive at the time of data analysis or who are lost to follow up, OS time will be censored at the last recorded date that the subject is known to be alive (date of last contact,

last visit date, date of last trial treatment administration or date of last scan, whichever is the latest) as of the data cut-off date for the analysis.

In Part B, BOR as determined by IERC will be defined in the same was as in Part A (see Section 8.3.1).

Other secondary endpoints include serum titers of anti-avelumab antibodies (ADA) and PK profile (sparse sampling).

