7.1.2.1 Part A

During the treatment period, the following assessments will be performed (see [Appendix I](#) for the detailed schedule):

- The EQ-5D and FACT-M will be completed by subjects prior to any study related procedures at Week 7, and then once every 6 weeks thereafter while on treatment.
- Subject interviews (optional) by a trained experienced interviewer to collect subjects' current experience with their disease and its treatment (at Week 13 and at 6 months of treatment, see [Section 7.7.1](#)).
- AEs and concomitant medications will be documented at each trial visit.
- ECOG PS will be assessed at Day 1 (unless the Screening ECOG PS was performed within 3 days prior to Day 1) and at each study visit thereafter.
- Physical examinations will be performed at each treatment visit until Week 13 and every 6 weeks thereafter. Such examinations will include a comprehensive skin examination for tumor.
- Vital signs and body weight will be assessed in each treatment visit.
- A 12-lead ECG (assessed prior to infusion and 2 hours \pm 20 minutes after the end of infusion) will be assessed at each treatment visit up to and including Week 13, and every 6 weeks thereafter until 18 months, after which subjects no longer require on treatment ECGs.
- The laboratory hematology, hemostaseology will be assessed at each visit. Core serum chemistry tests will be assessed at Weeks 1, 7, 9, and 11 and after Week 13, every 2 weeks thereafter and full serum chemistry (including core chemistry) will be assessed at Weeks 3, 5, and 13 and then every 6 weeks thereafter. In addition, for subjects with liver metastases at Baseline, samples for ALT, AST, total bilirubin, and alkaline phosphatase determination will be collected at Weeks 2, 4, and 6. A basic urinalysis (dipstick) will be performed at each on treatment visit. If the basic urinalysis is abnormal, a full urinalysis should be performed.
- A urine β -HCG pregnancy test will be performed at each treatment visit (before each administration of the study drug) for females of childbearing potential.
- Tumor evaluation (see [Section 7.3](#)) will be performed at Week 7, and then once every 6 weeks thereafter, with a tumor assessment visiting time window of 5 days prior to dosing. After Week 55 (12 months) from the first treatment, tumor assessments will be every 12 weeks.

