7.1.5 Post Treatment Follow-up

Subjects with an ADR ongoing at the End-of Treatment visit must be followed up until the ADR resolves, becomes stable, or is considered not clinically significant by the Investigator. In addition, subjects will be followed for any AE suspected to be related to trial treatment, especially for the occurrence of new autoimmune events up to 3 months after the last dose of avelumab.

For subjects who discontinue treatment prior to Week 13, off-treatment interviews (optional for both Part A and Part B) will be scheduled for 13 weeks and 6 months from the start of treatment to collect subjects' current experience with their disease, the study drug, and their experience within the trial. In case of discontinuation later than Week 13 but prior to 6 months of treatment, an off-treatment interview (optional for both Part A and Part B) will be scheduled for 6 months from the start of treatment.

For Part A, subjects without PD at the End-of-Treatment visit will be followed up for disease progression until PD (CT / MRI scans every 6 weeks until Week 55 [12 months] after the first study drug administration, then every 12 weeks using the same procedures and review as while on treatment; for trial sites in Germany, only MRI is to be used). CCI [REDACTED]

For Part B, subjects without PD at the End-of-Treatment visit will be followed for disease progression until PD (CT / MRI scans every 6 weeks until Week 55 [12 months] after the first study drug administration, then every 12 weeks).

After the End-of-Treatment visit, subjects will be followed quarterly for survival (including assessment of any further tumor therapy). The survival follow-up will continue for up to 5 years after the last subject receives the last dose of avelumab or last subject dies, whichever occurs earlier (see Section 5.7 for details of the end of study).

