		V1	V2	V3	V4	V5	V6	V7	V8	V9	V10				Until Progression	Up to 7 / 28 Days after Last Treatment ^{c,d}	10 Weeks after Last Treatment	Every 3 months ^b
		W1	W2	W3	W4	W5	W6	W7	W9	W11	W13							
		D1	D8	D15	D22	D29	D36	D43	D57	D71	D85							
Tumor evaluation / staging (CT Scan / MRI / mapping skin lesions / tumor markers / other established methods) ^{n,o}	X							X			X	6 weekly up to 12 months then 12 weekly	- /X		X			
Documentation of AEs and concomitant medication	X	X	X	X	X	X	X	X	X	X	X	2 weekly	x/X	X	X			
ACTH, ANA, ANCA, RF, free T4, and TSH	X										X	Week 25 and as indicated	- /X	X				
PK sampling ^p		X ^p		X ^p		X ^p		X ^p	X ^p	X ^p	X ^p	Weeks 15 and 25 ^p then every 12 weeks		X ^p				
ADA sampling ^q		X		X		X		X			X	6 weekly	- /X					
Pretreatment and study drug administration ^f		X		X		X		X	X	X	X	2 weekly						

CCI

Tumor tissue (biopsy) ^t	X														
------------------------------------	---	--	--	--	--	--	--	--	--	--	--	--	--	--	--

CCI

ACTH=adrenocorticotropic hormone, ADA=antidrug antibody, AE=adverse events, ALT=alanine aminotransferase, ANA=antinuclear antibody, ANCA=antineutrophil cytoplasmic antibody, AST=aspartate aminotransferase, β-HCG=β-human chorionic gonadotropin, BUN=blood urea nitrogen, CR=complete response, CT=computer tomography, ECG=electrocardiogram, ECOG PS=Eastern Cooperative Oncology Group Performance Status, EQ-5D=EuroQol-EQ-5D, FACT-M=functional assessment of cancer therapy-melanoma, HBV=hepatitis B virus, HCV=hepatitis C virus, HIV=human immunodeficiency virus, MCV=Merkel cell polyoma virus, MRI=magnetic resonance imaging, PK=pharmacokinetics, PR=partial response, RECIST=Response Evaluation Criteria in Solid Tumors version 1.1, RF=rheumatoid factor, SAE=serious adverse event, T4=free thyroxine, TSH=thyroid-stimulating hormone.

- a A time window of up to 3 days before or 1 day after the scheduled visit day (-3/+1 days) will be permitted for all trial procedures.

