16.2.2 Progression Free Survival (IERC)

The PFS time, according to the RECIST 1.1, will be defined as time from first administration of trial treatment until first observation of PD or death when death occurs within 12 weeks of the last tumor assessment or first administration of trial treatment (whichever is later). Details on determination of the first disease progression date are specified in the IERC charter.

Specific censoring rules are defined in Table 3 and Table 4. Last adequate tumor assessment is defined as the last tumor assessment result that is not “NE” or “NA”.

PFS time (in months) is defined as:

(date of PD or death - date of the first dose of study treatment + 1)/30.4375 (months).

For subjects with both of the following conditions fulfilled, the general censoring rules apply as presented in Table 3.

- Baseline tumor assessment
- At least one adequate tumor assessment after start of treatment

Table 3 General Censoring Rules for Progression-free Survival

| | | | Date of event / censoring | Censoring |
|--|---|-----|--|------------------|
| PD according to RECIST as assessed by the IERC | | | Date of PD | No |
| No PD | Death within 12 weeks after last tumor assessment or date of first study treatment (whichever is later) | Yes | Date of death | No |
| | | No | Date of last adequate tumor assessment | Yes |

IERC=Independent Endpoint Review Committee, PD=progressive disease.

For subjects with no tumor assessment at baseline or no tumor response assessment post-baseline, the special censoring rules as presented in Table 4, which overrule the general censoring rules, apply.

Table 4 Special Case Censoring Rules for Progression-free Survival

| | | | Date of event / censoring | Censoring |
|--|---|-----|----------------------------------|------------------|
| No tumor assessment at Baseline | Death within 12 weeks after first study treatment | Yes | Date of death | No |
| | | No | Date of first study treatment | Yes |
| No tumor response assessment post Baseline | Death within 12 weeks after first study treatment | Yes | Date of death | No |
| | | No | Date of first study treatment | Yes |

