16.2.4 Progression Free Survival

The PFS time, according to the RECIST 1.1, is defined as time from first administration of study treatment to the date of the first documentation of objective PD or death due to any cause, whichever occurs first.

PFS time (in months) is defined as:

$$(\text{date of event or censoring} - \text{date of first dose of study treatment} + 1) / 30.4375$$

PFS data will be censored on the date of the last adequate tumor assessment for subjects who do not have an event (PD or death), for subjects who start a new anti-cancer therapy prior to an event or for subjects with an event after two or more missing tumor assessments. Subjects who do not have a baseline tumor assessment or who do not have any post-baseline tumor assessments will be censored on the date of the first study treatment unless death occurred on or before the time of the second planned tumor assessment in which case death will be considered an event. Details on determination of the first disease progression date are specified in the IERC charter.

If a tumor assessment was performed on the same day as the start of a new anti-cancer therapy, it will be assumed that the tumor assessment was performed prior to the start of the new anti-cancer therapy; therefore, this tumor assessment will be included in the derivation of the PFS time.

The censoring and event date options to be considered for the PFS and DR analysis are presented in [Table 4](#). Last adequate tumor assessment is defined as tumor assessment result that is not “NE” or “NA”.

Table 4 Outcome and Event Dates for PFS and DR Analyses

| Scenario | Date of event / censoring | Outcome |
|--|--|---|
| No baseline assessment | Date of first study treatment | Censored ^a |
| Progression or death \leq xx weeks after last tumor assessment or \leq xx weeks after treatment start date, where xx is 12 weeks through 12 months from start of treatment, and 24 weeks thereafter. | Date of progression or death | Event |
| Progression or death $>$ xx weeks after the last tumor assessment, where xx is 12 weeks through 12 months from start of treatment, and 24 weeks thereafter. | Date of last adequate tumor assessment | Censored |
| No progression | Date of last adequate tumor assessment | Censored |

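### Part A keeps a 12-week death window after scans become 12-weekly, so after month 12 a death following one missed scan is censored, which can bias late PFS and duration of response upward

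*Protocol*

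**What the plan says.** **Part A scans.** Protocol 7.1.2.1 sets 6-weekly scans from Week 7, and then: "After Week 55 (12 months) from the first treatment, tumor assessments will be every 12 weeks". Section 7.1.5 extends this to subjects off treatment without progression ("then every 12 weeks using the same procedures and review as while on treatment"). The Part A table in Appendix I agrees: "6 weekly up to 12 months then 12 weekly".

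**Part A death window.** Protocol 8.3.2 ends a response at progression or "death within 12 weeks of the last tumor assessment, whichever occurs first". The PFS definition uses the same 12 weeks. Table 9 counts a death inside the window as an event and otherwise censors at the last known assessment: "If death not within 12 weeks after last tumor assessment or first administration of trial treatment". Progression documented by the IERC is an event whatever the gap since the previous scan. Part A SAP 16.2.1 (duration of response) and Table 3 in 16.2.2 (PFS) also use a fixed 12 weeks. None of these places changes the window after month 12.

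**Part B, on the same scan schedule.** Table 11 sets a window of xx weeks, "where xx is 12 weeks through 12 months from start of treatment, and 24 weeks thereafter". Part B SAP 16.2.4 gives the principle in words: PFS is censored "for subjects with an event after two or more missing tumor assessments".

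**Text that disagrees on the schedule.** Part A SAP Section 6 describes 6-weekly scans with no later change. Footnote b to the Part A schedule in Appendix I gives 6-weekly scans after the end of treatment, against Section 7.1.5.

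**The concern.** A window of this kind is meant to drop deaths that come after a long stretch without tumour assessment. Measured in scan intervals, the Part A window halves at month 12 without any stated reason.

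A subject who is failing is more likely to miss a scan and more likely to die soon. Censoring that subject at the last good scan treats them like those who remain under observation, so the censoring is informative. Because progression counts after any gap, only deaths are dropped.

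The protocol synopsis continues progression follow-up until 5 years after the last subject's last dose, so the 12-weekly phase supplies the whole late part of both curves. At stake is the description of how long benefit lasts in Part A.

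**Working it through.** The plan states no figure on this point, so the check is schedule arithmetic followed by an illustration.

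**1. Window divided by scan interval**

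| | Through month 12 | After month 12 |
|---|---|---|
| Part A | 12/6 = 2 | 12/12 = 1 |
| Part B | 12/6 = 2 | 24/12 = 2 |

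**2. Worked cases (Part A)**
- Last scan Week 43, Week 49 missed: the window ends at 43 + 12 = Week 55, when the next scan is due. A death in between is an event.
- Last scan Week 55, Week 67 missed: the window ends at 55 + 12 = Week 67. A death in Weeks 67 to 79 is censored at Week 55. With 24 weeks the window would end at Week 79 and the death would be an event.
- Transition: last scan Week 49, Week 55 missed. The window ends at Week 61, before the next due scan at Week 67.

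**3. No scan missed.** Protocol 7.1.2 allows a scan up to 5 days early. A scan 5 days early and the next on its planned day are 84 + 5 = 89 days apart, against a window of 84 days. A death on days 85 to 89 can then be censored although no scan was missed.

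**4. Which summaries are reached.** The affected deaths come after Week 67 (after Week 61 in the transition case).
- PFS is summarised at 3, 6 and 12 months, all earlier. The 12-month value can change only through a slightly smaller risk set.
- For 12-month duration of response, such a death must fall within 52 weeks of the first response: 67 − 52 = 15, so only responses first seen after about Week 15 (the Week 19 scan or later) are exposed. In the transition case, 61 − 52 = 9, so the Week 13 scan or later.
- The late curves, and possibly the medians, are exposed more widely.

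**5. Effect of one death.** A death with n subjects at risk lowers the Kaplan-Meier estimate by 1/n of its current value. Censoring it removes that step: 10% with 10 at risk, 5% with 20, 3.3% with 30 (n assumed).

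**6. Illustration.** The documents give no rates, so all inputs are assumptions. Subjects are progression-free at Week 55, with a 25% annual risk of progression and a constant annual risk of death. Scans are 12-weekly and missed independently of outcome. There were 8,000 simulated subjects per cell, so the second decimal is rough. Entries are the PFS estimate 52 weeks after Week 55 under the 12-week window minus that under the 24-week window, in percentage points.

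| Scans missed | Death risk 5%/year | 10%/year | 20%/year |
|---|---|---|---|
| 0% | 0 | 0 | 0 |
| 5% | 0.05 | 0.12 | 0.51 |
| 10% | 0.25 | 0.49 | 0.92 |
| 20% | 0.47 | 0.89 | 1.58 |
| 30% | 0.75 | 1.23 | 2.42 |

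In the largest cell the estimates are 65.92% and 63.50%. Where scans are missed, between 0.05 and 1.87 deaths per 25 subjects are reclassified over 156 weeks. If deterioration causes the missed scans, the differences would be larger.

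**The case against.** The case for leaving the rule alone has four parts.

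- PFS and duration of response in Part A are secondary, and Part A SAP Section 11 calls everything beyond the primary test exploratory. The ORR test does not use the window, OS counts every death, and response status at 6 and 12 months counts death without any window.
- On the 6-weekly schedule that the Part A SAP describes, 12 weeks is two intervals, so the rule was coherent where it was written.
- Part A SAP version 3.0 is dated 31 March 2016, and Protocol 10.6.2 already cites two published reports of Part A, one after at least 1 year of follow-up. Changing the main rule now would be post hoc.
- After a long gap, the date of death may itself be late as a progression date.

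The first part stands and limits the importance of the point. The second explains the mismatch but does not remove it, because the current protocol moves to 12-weekly scans. The third stands for analyses already run and decides the form of the fix. The fourth is a fair reason for having a window, but not for narrowing it in scan intervals at month 12, nor for applying it to deaths while progression after any gap counts.

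**Conclusion.** The point holds for late, descriptive Part A results. After month 12, a death without prior documented progression is censored after one missed scan, or on days 85 to 89 after an early scan. The late PFS and duration-of-response curves can be biased upward from such a death onward, as can possibly the medians and the 12-month duration of response of later responders. The size is unknown. The 0 to 2.4 points above rest on assumed rates and on scans missed independently of outcome; with no missed scans and exact timing the effect is zero.

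A reader might infer more than the documents support:
- *That the 12-month PFS result is inflated.* The affected deaths fall later than that landmark.
- *That every death 85 to 168 days after the last scan is censored in Part A and counted in Part B.* A death after documented progression is irrelevant in both parts, and Part B censors at new anticancer therapy whenever death follows.
- *That this rule alone makes the two parts non-comparable, always in favour of Part A.* Table 9 counts progression after any gap and has no censoring for new therapy, so on those points Part A counts more events. The populations also differ, and no comparison of PFS or duration of response between the parts is planned in the available text.

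**What to change.** 1. For deaths only, set the window at 12 weeks through month 12 and 24 weeks thereafter in Protocol 8.3.2 and Table 9, the matching synopsis text, and Part A SAP 16.2.1 and 16.2.2 (Table 3). Do not adopt Table 11 wholesale: it would also bring in Part B's censoring of late progression.
2. State whether the date of the last scan or the date of death decides which window applies. Table 11 leaves this open, and it settles the Week 49 case above.
3. For Part A analyses already run, keep the main rule, add the wider window as a labelled sensitivity analysis, and report how many deaths are reclassified.
4. Reconcile the scan wording in Part A SAP Section 6 and in footnote b of the Part A schedule with Protocol 7.1.2.1 and 7.1.5. The 24 weeks follow from the 12-weekly interval, so the window must match the reconciled schedule.

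The cost is a small protocol and SAP text change and one re-run of existing data. No new data are needed. Late PFS and duration of response may become slightly less favourable.
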